HRQoL instruments (European Organization for Research and Treatment of Cancer Quality of Life Questionnaire-Core 30 [EORTC QLQ-C30]) will be administered pre-dose on C1D1 and subsequent assessments will occur at the same cycle visits as disease assessments until EOT. For MTC patients with diarrhea present at baseline, bowel assessments will be collected pre-dose C1D1, weekly for the first cycle, and at D1 of each cycle until EOT.

STUDY ENDPOINTS:

Primary Endpoint:

- ORR based on RECIST v1.1 assessed by IRC.

Secondary Endpoints:

- Parameters of anti-tumor activity/clinical benefit, including: ORR (by Investigator), DOR (by IRC and Investigator), CNS ORR (by IRC), CNS DOR (by IRC), TTR (time to response), TTBR (time to best response by IRC and Investigator), CBR (by IRC and Investigator), PFS (by IRC and Investigator), and OS.
- Frequency, severity, and relatedness of treatment-emergent adverse events (TEAEs) and Serious Adverse Events (SAEs), changes in hematology and blood chemistry values, assessments of physical examinations, vital signs, and ECGs.

- Plasma concentrations of seliperatinib and PK parameters, including, but not limited to, AUC_{0-24} , C_{max} , and T_{max} .

Exploratory Endpoints:

- Differences in efficacy and safety based on seliperatinib PK parameters.
- Changes in CEA and calcitonin (for patients with MTC), thyroglobulin (non-MTC patients), ACTH and cortisol (patients with Cushing's disease related to their cancer) with seliperatinib treatment.
- Changes from baseline in disease-related symptoms and HRQoL, as measured by EORTC QLQ-C30 (adults), and patient bowel diaries (MTC patients only).
- Time from PD₁ to PD₂ for patients who continue to receive study treatment beyond disease progression.

STATISTICAL METHODS:**Safety Analyses:**

The safety population will consist of all enrolled patients who receive at least one dose of seliperatinib. A baseline measurement and at least one laboratory or other safety-related measurement obtained after treatment of study drug may be required for inclusion in the analysis of a specific safety parameter.

Efficacy Analyses:

The efficacy analysis will be conducted on all treated patients enrolled in Cohort 1 and 2 who have confirmed *RET* fusion positive solid tumor or *RET* mutant MTC by central lab, respectively.

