6.4.1 Discontinuation of Inadvertently Enrolled Patients

If Lilly or the investigator identifies a patient who did not meet enrollment criteria and was inadvertently enrolled, a discussion must occur between the Lilly CRP and the investigator to determine if the patient may continue in the study. If both agree it is medically appropriate to continue, the investigator must obtain documented approval from the Lilly CRP to allow the inadvertently enrolled patient to continue in the study with or without study drug. Patients who are discontinued from study drug will have follow-up procedures performed as shown in the Schedule of Activities (Table 7-1).

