9.2 Analysis Populations

Enrolled population: will include all enrolled patients.

Treated population will include all enrolled patients who received at least one dose of selpercatinib. This population will be used for safety analysis and efficacy analysis other than primary efficacy analysis.

Primary efficacy analysis population: will include all treated patients enrolled in Cohort 1 and 2 who have confirmed RET fusion positive solid tumor or RET mutant MTC by central lab, respectively. The primary efficacy analysis will be conducted on this population.

Pharmacokinetic population will include all treated patients with baseline and at least one postbaseline evaluable PK sample.

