9.4.2 Safety Analyses

Safety will be assessed by clinical review of all relevant parameters including AEs, SAEs, laboratory values, vital signs, ECG results, concomitant medications, and thyroid function. Unless specified otherwise, the safety analyses will be conducted for the safety population defined in Section 8.2 from all cohorts. Tabulations will be provided by cohort and overall.

Summary tables and listings will be provided for all reported TEAEs, defined as AEs that start on or after the first administration of study drug. The reported AE term will be assigned standardized coding using MedDRA; the MedDRA version shall be specified in study documents.

TEAEs will be summarized based on the number and percentage of patients experiencing the event by MedDRA System Organ Class (SOC) and preferred term (PT). The causal relationship between the occurrence of an AE and study drug will be judged by the Investigator based on the conventions described in Section 8.2. In the event a patient experiences repeat episodes of the same AE, then the event with the highest severity grade and strongest causal relationship to study drug will be used for purposes of incidence tabulations.

Tabular summaries will be provided for:

- All TEAEs.
- TEAEs by relationship (yes, no) to underlying disease, other medical conditions or concomitant medications, and maximum severity grade.
- TEAEs with action of study drug delayed/interrupted or treatment reduced.
- TEAEs with action of study drug discontinued.
- All SAEs.
- SAEs by relationship (yes, no) to underlying disease, other medical conditions, or concomitant medications.

All deaths including on-study death that occur within 28 days of treatment discontinuation will be reported in a patient listing, which will include the primary cause of death and the number of days

between the date of the last dose of study drug and death. A summary of the anticancer therapies received after discontinuation of study drug will be provided.

Hematology and serum chemistries will be summarized in a descriptive manner by calculating the mean, standard deviation, median, and range.

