6.1. General Considerations

6.1.1. Analysis Populations

Entered population: will include all patients who signed the informed consent form

Enrolled population: will include all eligible patients.

Safety population: will include all enrolled patients who received at least one dose of selpercatinib. This population will be used for safety analysis.

Primary efficacy analysis population/primary analysis set (PAS): will include all treated patients enrolled in Cohort 1 and 2 who have *confirmed* RET fusion positive solid tumor or RET mutant MTC by central lab, respectively. The primary efficacy analysis will be conducted on this population.

Per-protocol population: will include all patients in the primary efficacy analysis population who are compliant with the study protocol without major protocol violations.

CNS response analysis population: will include all treated patients in Cohort 1 with confirmed *RET*-fusion positive solid tumor who have IRC-assessed CNS metastases at baseline.

Baseline diarrhea population: will include patients in Cohort 2 who had diarrhea at baseline. All analyses of bowel diary will be based on this population.

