6.6.4. Prior Therapies

The following variables will be summarized for all enrolled patients:

- prior systemic treatments (yes, no)
- prior radiotherapy (yes, no)
- prior cancer-related surgery (yes, no)
- type of prior systemic treatments (e.g., platinum-based chemotherapy, anti-PD-1/PD-L1 antibody, selective TKI inhibitors (EGFR, ALK, ROS1, etc), multikinase inhibitors (cabozantinib, vandetanib, etc), other prior systemic therapies)
- number of prior multikinase inhibitors used (0, 1, 2)
- number of prior systemic regimens (0, 1, 2, ≥ 3)
- number of prior systemic regimens (as a continuous variable)
- number of prior treatment lines (0, 1, 2, ≥ 3)
- best overall response to most recent prior systemic regimen (CR, PR, SD, PD, NE, unknown)

The number of prior treatment lines is defined as the number of distinct dates of progressive disease.

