6.12. Subgroup Analyses

If warranted by data, the point estimates of ORR (and 95% CI) and median DOR (and range)

based on IRC and investigator assessments will be calculated for the subgroups defined by the following:

- age (< 60 years, ≥ 60 years)
- sex (male, female)
- ECOG performance status at baseline (0, 1–2)
- smoking status (never smoked, current smoker, former smoker)
- *RET* fusion gene (KIF5B/CCDC6/NCOA4, other)
- *RET* mutation type (M918T, extracellular cysteine mutation, other)
- Prior systemic therapy use (treatment naïve vs pre-treated)
- type of prior systemic therapies (MKI including *RET*, other MKI, non-MKI)
- type of prior systemic therapies 2 (anti-PD-1/PD-L1 antibody, other)
- best overall response to most recent prior systemic therapy (CR, PR, SD, PD, NE)

Treatment naïve patients include patients who received no prior systemic therapies or who received only adjuvant/neo-adjuvant therapies; Otherwise, patients are categorized as pre-treated.

As a supportive analysis, ORR will be summarized on the **response evaluable subgroup**, defined as patients with measurable disease (at least 1 target lesion) and at least 1 post-baseline tumor assessment.

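### Taken literally, the SAP's Enrolled, Safety and prior-line definitions give wrong results, and criterion 15 and the non-primary efficacy populations need reconciling across the documents

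*SAP*

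**What the plan says.** **Populations for safety.** SAP 6.1.1 first lists an Entered population (everyone who signed consent). It then has "Enrolled population: will include all eligible patients" and "Safety population: will include all enrolled patients who received at least one dose of selpercatinib". Protocol 9.2 instead has "Enrolled population: will include all enrolled patients", and assigns safety to a Treated population: all enrolled patients with at least one dose. The protocol synopsis agrees: "The safety population will consist of all enrolled patients who receive at least one dose". Protocol 6.4.1 covers patients found not to have met the entry criteria and permits the sponsor's physician and the investigator "to allow the inadvertently enrolled patient to continue in the study with or without study drug". Protocol 9.4.2 says "the safety analyses will be conducted for the safety population defined in Section 8.2 from all cohorts", but Section 8.2 of the protocol is Safety Assessments and defines no population.

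**Prior lines.** SAP 6.6.4: "The number of prior treatment lines is defined as the number of distinct dates of progressive disease". The same section also reports the number of prior systemic regimens, both in categories and as a continuous variable. SAP 6.12 classes as treatment-naive "patients who received no prior systemic therapies or who received only adjuvant/neo-adjuvant therapies".

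**Criterion 15.** Protocol 4.1, criterion 15, requires Cohort 1 and 2 patients to have failed standard of care or not tolerated it. Protocol 3.4 also admits to Cohort 1 patients who turned down first-line standard therapy or whom the investigator judged unsuited to it. It opens Cohort 2 to patients whether or not they had earlier systemic treatment. Criterion 18 sets a condition for treatment-naive Cohort 2 patients, and Table 4-1 lists no approved standard of care for that cohort.

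**Non-primary efficacy.** SAP 6.9.1 puts the primary analysis of the efficacy endpoints on the primary analysis set (PAS: treated, centrally confirmed Cohort 1 and 2 patients) and supportive analyses on Enrolled. Protocol 9.2 puts all efficacy other than the primary analysis on Treated. Protocol 9.4.3 names an efficacy population that 9.2 does not define. The synopsis uses the same patients as the PAS.

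**The concern.** A safety set should hold every patient exposed to the drug. If one word makes exposure count only in eligible patients, the people most likely to be removed are those the protocol itself expects to be enrolled in error and kept on treatment. In a single-arm study of about 75 patients, one patient's events can be the only instance of a given term.

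The other three points are smaller but of the same kind: a rule that gives the wrong answer, or two rules that cannot both be followed. The line count describes how heavily pre-treated the cohorts were, which readers use when judging a response rate. Criterion 15 bears on who counts as a deviation. The population assignments fix the denominators of the supportive results and decide whether time-to-event endpoints can be derived for everyone included.

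**Working it through.** **1. Safety set.**

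Inputs: overall sample size 75 and true event rates of 2% and 5% (protocol 9.3, SAP 5.2). The number of dosed ineligible patients is not given; one is assumed for illustration.

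- Plan's own figure first. P(at least one event) = 1 − (1 − p)^n. At n = 75: 1 − 0.98^75 = 78.0% and 1 − 0.95^75 = 97.9%. The plan states approximately 80% and 98%, so both reproduce to within 2 points.
- One patient removed, n = 74: 1 − 0.98^74 = 77.6% and 1 − 0.95^74 = 97.8%. The smaller denominator hardly matters.
- The loss is the patient's own events. An event seen only in that patient goes from 1/75 = 1.3% (exact 95% CI 0.0 to 7.2%) to 0/74 = 0% (0 to 4.9%).
- With no dosed ineligible patient, nothing changes.

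**2. Prior lines.** Apply the SAP 6.6.4 rule to simple histories:

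- One regimen, stopped for intolerance without progression: no progression date, so 0 lines.
- Two regimens, one ended by progression and one by intolerance: one date, so 1 line.

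Such histories are expected, because protocol 3.4 and criterion 1 admit patients intolerant of earlier therapy. One miscounted patient moves a category of the row by 1/20 = 5.0 points in a cohort of the minimum size, and by 1/75 = 1.3 points overall.

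**3. Criterion 15 beside the cohort definitions.** No arithmetic applies.

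- Cohort 1: a patient who declined first-line therapy satisfies protocol 3.4 and does not satisfy criterion 15. The conflict is direct.
- Cohort 2: with no standard of care listed, criterion 15 either cannot be met or asks for nothing. If it cannot be met, it excludes the treatment-naive patients for whom protocol 3.4 and criterion 18 provide. If it asks for nothing, it is redundant for this cohort.

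**4. Populations for efficacy.** SAP 6.9.1 (PAS for the primary analysis of endpoints) and the synopsis agree. The remaining mismatch is Treated in protocol 9.2 against PAS and Enrolled in SAP 6.9.1, plus the undefined name in 9.4.3.

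Enrolled and Treated can differ, since protocol 6.6 mentions enrolled patients who receive no drug. Progression-free survival (PFS) and overall survival (OS) run from the first dose (SAP 6.9.7 and 6.9.8). Even the PFS rule for patients with no post-baseline assessment censors at the first-dose date, which a never-dosed patient does not have.

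For the supportive ORR, with counts assumed because the documents give none, take 10 responders among 20 treated patients:

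- No never-dosed patient: 10/20 = 50.0%, exact 95% lower limit 27.2%.
- One added: 10/21 = 47.6%, lower limit 25.7%.
- Two added: 10/22 = 45.5%, lower limit 24.4%.

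**The case against.** **Safety.** The context favours a harmless meaning. Enrolled follows directly after Entered, so *eligible* may serve only to separate enrolled patients from screen failures. Protocol 6.4.1 itself calls the wrongly admitted patient enrolled, and the SAP's Safety sentence closely tracks the protocol's Treated sentence. This stands as a plausible intention, but the SAP does not state it and a programmer works from the definition. A reader might also infer from the Section 8.2 reference that the protocol leaves the safety set undefined. It does not: protocol 9.2 and the synopsis settle it, and the reference is simply wrong.

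**Prior lines.** The regimen rows in SAP 6.6.4 still show therapy stopped for intolerance, so the information is not lost. That stands and limits the damage to one row. A reader might go further and say that treatment-naive Cohort 2 patients are overcounted through the progression required by criterion 18. That would need this date to be counted, which the SAP does not say.

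**Criterion 15.** With no standard of care to fail, Cohort 2 may involve no practical contradiction. That stands. A reader might expect patients to drop out of the per-protocol set. This would require a logged deviation, its classification as major, and use of a set that SAP 6.13 makes optional.

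**Efficacy.** It is tempting to say that non-primary efficacy has no agreed population at all. SAP 6.9.1 does not support that: PAS is the main layer and Enrolled an additional one. The protocol also defers detail to the SAP, and protocol Section 5 says that every patient meeting the criteria will receive drug, so never-dosed patients may be few or none.

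**Conclusion.** The concern holds as a set of wording defects that should be corrected.

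- **Two SAP rules give wrong results if followed as written.** The eligibility word in 6.1.1 removes a dosed ineligible patient's events; the size is zero if there is no such patient, and the one-patient example is an assumption. The line rule in 6.6.4 counts a regimen stopped for intolerance as zero, affecting one descriptive row only.
- **Two sets of passages do not agree.** Criterion 15 conflicts with the Cohort 1 definition and is unmeetable or empty for Cohort 2. Protocol 9.2 and 9.4.3 differ from SAP 6.9.1 on non-primary efficacy, with no derivation rule for never-dosed patients. The ORR shifts shown for the latter rest on assumed counts.

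A reader might infer that the main result is at risk. The documents do not support that: the primary ORR uses the PAS, which SAP 6.1.1 and protocol 9.2 define in the same terms, and the treatment-naive versus pre-treated split in SAP 6.12 does not use the line count. No stated figure is disputed.

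**What to change.** 1. **SAP 6.1.1 and protocol 9.4.2.** Define Enrolled as in protocol 9.2, without an eligibility condition, and state that Safety includes every patient who took at least one dose. Correct the Section 8.2 cross-reference and use one name for the set that the protocol calls both Treated and safety.
2. **SAP 6.6.4.** Derive lines from distinct prior systemic regimens for advanced disease, whatever the reason for stopping, and treat adjuvant and neo-adjuvant therapy as SAP 6.12 does. That handling is what distinguishes this row from the regimen row.
3. **Protocol 4.1.** Reconcile criterion 15 with the Cohort 1 and 2 definitions in 3.4, criterion 18 and Table 4-1. Which eligibility rule governs is for the sponsor to decide.
4. **Protocol 9.2 and 9.4.3 with SAP 6.9.1.** Make the assignments agree, keeping the PAS and supportive layers as separate analyses. Base endpoints timed from first dose, such as PFS and OS, on treated patients, or state how they are derived for patients never dosed.

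The cost is a SAP wording change and a protocol clarification. Regimens are already summarized under SAP 6.6.4, so no new data are needed.

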3.4 Investigational Plan

For this China-specific protocol, it is expected that at least 20 patients in each Cohort 1 and Cohort 2, and up to 25 patients in Cohort 3 with advanced solid tumors with evidence of a *RET* gene alteration in tumor and/or blood (e.g., gene rearrangement fusions and/or mutations, excluding synonymous, frameshift, or nonsense mutations) will be enrolled to one of three cohorts (Figure 3-1) as noted below to better characterize the safety and efficacy of selpercatinib in patients with specific abnormalities in *RET*. For Cohort 1 and 2, evidence of a *RET* gene alteration in tumor (i.e., not just blood) as defined in Table 3-1 is required (a positive germline test for a *RET* mutation is acceptable for patients with MTC).

Enrollment will be based on tumor type, type of *RET* alteration, and prior treatment:

- Cohort 1: Advanced *RET* fusion-positive solid tumor progressed on or intolerant to ≥ 1 prior standard therapy, or patients who declined or not suitable for standard first line therapy in the opinion of the Investigator (refer to Table 4-1 for standard therapies). For lung cancer, only patients harboring *RET-KIF5B*, *RET-CCDC6*, *RET-NCOA4* can be enrolled in Cohort 1. For other solid tumors, patients with any *RET* fusions can be enrolled in Cohort 1.
- Cohort 2: Advanced *RET*-mutant MTC with or without prior systematic therapy
- Cohort 3: Advanced *RET* altered solid tumor
 - Cohorts 1-2 without measurable disease;
 - Other *RET*-altered solid tumor or other *RET* alteration/activation not meeting the requirements for Cohorts 1 or 2;
 - MTC syndrome spectrum cancers (e.g. MTC, pheochromocytoma) with neuroendocrine features/differentiation or poorly differentiated thyroid cancers with other *RET* alteration/activation may be allowed with prior Sponsor approval;
 - Known cfDNA positive for a *RET* gene alteration and not able to be determined in tumor or FISH positive in tumor without PCR/NGS result may be allowed with prior Sponsor approval.

Selpercatinib will be administered in oral form at 160 mg BID. Each cycle will consist of 28 days.

Primary endpoint: ORR per RECIST 1.1 by independent review committee.

Secondary endpoint: ORR per RECIST 1.1 by investigator, DOR, CNS ORR, CNS DOR, CBR, TTR, TTBR, CBR, PFS, OS, PK, safety

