16. Cohorts 1-2: enrollment will be restricted to patients with evidence of a *RET* gene alteration in tumor (i.e., not just blood) as defined in [Synopsis Table 1](#) . However, a positive germline DNA test for a *RET* gene mutation as defined in [Appendix B](#) (Table 11-2) is acceptable in the absence of tumor tissue testing for patients with MTC.
17. Cohorts 1-2: at least one measurable lesion as defined by RECIST v1.1 and not previously irradiated (unless PD for the irradiated lesion[s] has been radiographically documented).
18. Cohort 2: radiographic PD within the previous 14 months for systematic treatment naïve patient.

Note:

Patients otherwise eligible for Cohort 2 who do not demonstrate radiographic PD within the previous 14 months may be enrolled to Cohort 3 if a compelling rationale is provided by the Investigator and approved by the Sponsor.

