- x. If not performed within the last 8 weeks.
- y. Patients who discontinue study drug for reasons other than PD (e.g., AE, noncompliance, etc.) may (but for practical reasons and to minimize patient inconvenience, are not required to) undergo additional disease assessment by imaging (as specified above until PD, withdrawal of consent or initiation of a new anticancer therapy(ies)).
- z. Confirmatory scans: Minimum of 4 weeks (e.g., 28 days) after the first tumor evaluation showing a CR or PR by RECIST 1.1, if permitted by regulatory authorities. The next scan should continue according to the schedule above.
- aa. For 12 subjects in intensive PK testing, PK test performed on C1D1: Up to pre-dose, and post-dose 1 hour (± 15 minutes), 2 hours (± 15 minutes), and 4 hours (± 15 minutes), 8 hours (± 30 minutes) and 12 hours (± 30 minutes), C1D8: Up to pre-dose, and post-dose 1 hour (± 15 minutes), 2 hours (± 15 minutes), and 4 hours (± 15 minutes) and 8 hours (± 30 minutes).
- bb. For all enrolled subjects in PopPK testing, PK test performed on each cycle D1 predose.

- cc. EORTC QLQ-C30. The questionnaires should be answered by the subject to the best of his/her ability, prior to receiving drug on C1D1 and preferably prior to learning the results of the radiologic disease assessment for subsequent cycles.
- dd. Only for patients with a diagnosis of MTC and diarrhea at baseline. Two patient bowel diary cards will be dispensed on C1D15. The questionnaires should be answered by the subject to the best of his/her ability.
- ee. AEs and SAEs should be recorded from the time that written informed consent has been obtained through the SFU Visit.
- ff. Concomitant, ongoing medication(s) plus those administered within 14 days prior to the planned start of treatment.
- gg. Patients will be followed for survival status, date of progression, and subsequent anticancer therapy(ies) by telephone or other method.

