7.7.4 Collection of EORTC QLQ-C30 and Bowel Diary

Paper Quality of Life (QoL) instruments will be administered pre-dose on C1D1.

The EORTC QLQ-C30 and a bowel diary (for MTC patients only) will be used (refer to [Appendix J](#)) and should be implemented for newly enrolled patients. Only patients who have completed the questionnaire at baseline should complete subsequent questionnaires at the specified follow-up periods.

For EORTC QLQ-C30, subsequent assessments will occur at the same cycle visits as disease assessments until EOT. Each assessment should be performed before the subject learns the results of his or her restaging.

For MTC patients, the bowel diary assessments will be collected weekly on Cycle 1, and on Day 1 of every cycle thereafter through EOT. Inaccurate recording will not be considered a protocol violation.

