9.1.3 Exploratory Endpoints

- Differences in efficacy and safety based on selpercatinib PK parameters
- Changes in CEA and calcitonin (patients with MTC), thyroglobulin (non-MTC thyroid cancer patients), and ACTH and cortisol (patients with Cushing's disease related to their cancer) with selpercatinib treatment
- Changes from baseline in disease-related symptoms and HRQoL, as measured by EORTC QLQ-C30, and patient bowel diaries (MTC patients only)
- Time from PD₁ to PD₂ for patients who continue to receive study treatment beyond disease progression

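### SAP 6.1.1 puts every bowel-diary analysis on Cohort 2, although the protocol collects the diary by MTC diagnosis in any cohort and SAP 6.10.2 uses different populations

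*SAP*

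**What the plan says.** **SAP 6.1.1** defines a baseline diarrhea population that "will include patients in Cohort 2 who had diarrhea at baseline. All analyses of bowel diary will be based on this population".

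**The protocol's collection rule** depends on diagnosis. The Synopsis reads "For MTC patients with diarrhea present at baseline, bowel assessments will be collected pre-dose C1D1, weekly for the first cycle". Note dd to Table 7-1 reads "Only for patients with a diagnosis of MTC and diarrhea at baseline". Section 7.7.4 is wider still: "For MTC patients, the bowel diary assessments will be collected weekly on Cycle 1, and on Day 1 of every cycle thereafter through EOT", with no mention of baseline diarrhea. The exploratory endpoint in 9.1.3 is likewise limited to MTC patients and not to a cohort.

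**Routes by which MTC patients reach Cohort 3.** Protocol 3.4 lists "Cohorts 1-2 without measurable disease", which takes in RET-mutant MTC. The note to inclusion criterion 18 in 4.1 says: "Patients otherwise eligible for Cohort 2 who do not demonstrate radiographic PD within the previous 14 months may be enrolled to Cohort 3", given a rationale and Sponsor approval. Section 3.4 also admits MTC-spectrum cancers with other RET alteration or activation, and patients positive only in cfDNA, both with Sponsor approval.

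**SAP 6.10.2** gives its own populations. By-visit summaries cover all patients, with a separate display for those with diarrhea at baseline. Change from baseline covers treated patients with a baseline and a later assessment. Time to first improvement uses the baseline diarrhea population. Time to first worsening uses the whole of Cohort 2.

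**The concern.** The protocol asks an MTC patient with baseline diarrhea to keep the diary whether that patient sits in Cohort 2 or Cohort 3. The analysis population then depends on cohort, and the SAP gives no reason for the restriction. What sends an MTC patient to Cohort 3 (measurability, recency of progression, type of alteration or assay) does not prevent a diary from being scored.

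Two things are at stake. The endpoint named in Protocol 9.1.3 would be answered in only part of the group from which it was collected, and that group is already small because baseline diarrhea is required. Separately, 6.1.1 and 6.10.2 cannot both be programmed as written, so the population behind each diary table would be settled after the fact.

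**Working it through.** The plan has no figure to reproduce here. The check is a comparison of text, followed by bounds on the number affected.

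**Step 1: who completes a diary, and who is analysed.**

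| Source | Limited to Cohort 2? | Baseline diarrhea required? |
|---|---|---|
| Protocol Synopsis; Table 7-1 note dd | No (MTC) | Yes |
| Protocol 7.7.4 | No (MTC) | Not mentioned |
| SAP 6.1.1, all diary analyses | Yes | Yes |
| SAP 6.10.2, by-visit summaries | Not stated | No, plus a separate display if yes |
| SAP 6.10.2, change from baseline | Not stated | No |
| SAP 6.10.2, time to first improvement | Yes, through the 6.1.1 definition | Yes |
| SAP 6.10.2, time to first worsening | Yes | No |

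**Step 2: can 6.1.1 and 6.10.2 be reconciled?** Suppose the 6.10.2 by-visit summaries meant everyone in the 6.1.1 population. The separate display for those with baseline diarrhea would then be the same patients again, so the group must be wider than 6.1.1 allows. Time to first worsening goes further: 6.10.2 gives a censoring rule for Cohort 2 patients without baseline diarrhea, whom 6.1.1 excludes from every diary analysis. The two sections contradict each other.

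**Step 3: what happens to Cohort 3 MTC diaries?**
- Under 6.1.1 taken literally, they enter no analysis.
- Under 6.10.2, they can enter the by-visit and change-from-baseline summaries, because no cohort limit is stated there.
- Under either section, they are absent from time to first improvement and time to first worsening.

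**Step 4: bounds.** Protocol 9.3 caps Cohort 3 at 25 and sets Cohort 2 at 20 or more. The documents do not say how many Cohort 3 patients have MTC, so the number affected lies between 0 and 25.

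As an illustration only, let c2 and c3 be the MTC patients in Cohorts 2 and 3, and assume baseline diarrhea is equally common in both, so that its prevalence cancels. Share left out = c3/(c2 + c3). Ratio of standard errors, Cohort 2 alone against all MTC = √((c2 + c3)/c2). With c2 = 20:

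| c3 (assumed) | Share left out | SE ratio |
|---|---|---|
| 0 | 0/20 = 0% | √(20/20) = 1.00 |
| 5 | 5/25 = 20% | √(25/20) = 1.12 |
| 10 | 10/30 = 33% | √(30/20) = 1.22 |
| 25 (cap) | 25/45 = 56% | √(45/20) = 1.50 |

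A larger Cohort 2 lowers every row below the first. The ratios apply only where Cohort 3 is actually left out.

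**The case against.** A reader might infer from 6.1.1 that Cohort 3 diaries are never analysed. The documents do not support that: 6.10.2, the section that specifies the analyses, describes by-visit summaries and change from baseline with no cohort restriction, and both could include these patients. For the same reason it cannot be said that these patients keep diaries to no purpose, nor can a loss of precision be attached to the diary summaries as a whole.

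The size may also be nil. Except for patients without measurable disease, the Cohort 3 routes cited need Sponsor approval, and the recent-progression route also needs a compelling rationale, so low counts are plausible.

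Finally, cohort-based sets are normal in this SAP: the primary and CNS populations are limited by cohort too. Cohort 3 is mixed, and whether MTC patients without recent progression should be pooled for symptom change is a matter of judgement. The pooling of all MTC patients in SAP 6.9.1 is for supportive efficacy and does not oblige the sponsor to pool diaries.

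All of this limits the point, and a reasoned choice of Cohort 2 alone would be defensible. It does not remove the conflict between the two SAP sections, the omission of Cohort 3 MTC patients from both Kaplan-Meier analyses, or the absence of a stated reason for departing from the protocol's collection rule.

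**Conclusion.** The point holds as a mismatch between protocol and SAP together with an internal SAP contradiction. SAP 6.1.1 read literally excludes collected data that belong to the protocol's own endpoint; 6.10.2 is wider for the summaries; and the time-to-event analyses omit Cohort 3 MTC patients in any case.

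The size is unknown from the documents, from 0 to 25 patients. Any percentage depends on an assumed Cohort 3 MTC count, an assumed Cohort 2 size and equal prevalence of baseline diarrhea. The endpoint is exploratory and descriptive, and no primary or secondary conclusion depends on it. This is a desirable correction, not an essential one.

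**What to change.** 1. In SAP 6.1.1, define the baseline diarrhea population as all treated MTC patients, in any cohort, who had diarrhea at baseline.
2. Replace the sentence that places all diary analyses on that population with a pointer to 6.10.2.
3. In 6.10.2, name the population for each analysis: by-visit summaries, change from baseline, time to first improvement and time to first worsening. Use MTC patients across cohorts for all of them, and show Cohort 2 alone as a supportive row.
4. For time to first worsening, state whether patients without baseline diarrhea belong. Table 7-1 note dd does not collect a diary from them, whereas Protocol 7.7.4 does not exclude them, so those two passages need to be reconciled first.

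If the sponsor prefers Cohort 2 alone, the SAP should give the reason and still bring 6.1.1 and 6.10.2 into line.

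The cost is a few sentences in two SAP sections plus the clarification in item 4, with no new data collection. The downside is a slightly more mixed MTC group, which the Cohort 2 row makes visible.
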